3.2.4 Review of Echocardiographic Images by the Independent Echocardiographic Core Lab

The ECL will confirm subject's screening echocardiography images for TR severity eligibility criteria are met per the 2017 ASE guideline for TR grading²⁷, and defined in **Appendix VIII**. Subjects failing the criteria will be considered a screen failure and not allowed into the trial. Additionally, the ECL will be responsible for assessing TR severity and echocardiographic analyses at all visits (baseline and follow-ups) and operate according to the ECL Manual of Operations.

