4.3.6 Echocardiographic Endpoints

Echocardiographic endpoints will be assessed by the Echocardiography Core Laboratory (ECL) and reported at baseline, discharge, 30 day, 6 months, 1 year, 2 year, and 3 year postimplantation (unless indicated).

- o TR Severity Grade
- Effective Regurgitant Orifice Area (EROA)
- Regurgitant Volume
- Regurgitation Jet Area
- Vena Contracta Width
- o PISA Radius
- Inferior Caval Vein Diameter
- Tricuspid Annular Diameters (A-P and S-L)
- o Tricuspid Annular area
- Tricuspid Valve Area
- Tenting Area (At baseline only)
- Tenting Distance (At baseline only)
- o Tricuspid Leaflet Tethering Distance (At baseline only)
- o Right Ventricular End Diastolic Dimension (RVEDD)
- o Right Ventricular End Systolic Dimension (RVESD)
- Right Ventricular Fractional Area Change
- Right Ventricular Systolic Pressure (RVSP)
- Right Atrial Volume
- Tricuspid Annular Plane Systolic Excursion (TAPSE)
- o Right Ventricular Free Wall Strain
- o Mean Tricuspid Valve Gradient
- Cardiac Output
- Forward Stroke Volume (Left Ventricle)
- Left Ventricular Ejection Fraction (LVEF)
- Single Leaflet Device Attachment
- o Embolization of the TVRS Clip or TVRS System components
- Tricuspid Valve Stenosis

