6.8 Heart-Related Office Visits

A Heart-Related Office Visit eCRF should be completed if a subject is seen for a heart related reason at the investigational site or at any other facility. Information pertaining to adverse events, heart failure medication changes or hospitalizations, as appropriate, should also be collected.

If an echocardiographic imaging study is performed at any visit, whether or not it is a study related visit, echocardiography images should be submitted to the ECL in a timely manner.

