2. NON-CARDIOVASCULAR DEATH

Any death not covered by the VARC definitions of Cardiovascular Death, such as death caused by infection, malignancy, sepsis, pulmonary causes, accident, suicide, or trauma.

DEVICE EMBOLIZATION

Detachment of the deployed TVRS Clip from the tricuspid leaflets as assessed by the study site.

Diagnosis and management of any occurrence or suspected occurrence of device embolization will be per the site investigator's best medical judgment. Some recommendations for clinical diagnosis and management of device embolization include but are not necessarily limited to those outlined below:

- Diagnosis:
 - Observation of patient's clinical symptoms,
 - o Assessment of Clip status via TTE examination of valve, and/or
 - Fluoroscopy and/or x-ray imaging.
- **Management** will depend on the specific patient's clinical situation and will be determined by the site investigator's best medical judgment including assessment of overall risks and benefits of further intervention. Some methods of management to consider are:
 - o Continued regular clinical monitoring of the patient and the embolized device;
 - Transcatheter manipulation method(s) to stabilize device position;

(Version 2.0; 01 February 2018)

- Removal through percutaneous approach and/or
- o Removal through surgical approach.

DEVICE THROMBOSIS

Formation of an independently moving thrombus on any part of the TVRS Clip evidenced by echocardiography or fluoroscopy. If the TVRS Clip is explanted or an autopsy is performed, this diagnosis should be confirmed.

ENDOCARDITIS

A diagnosis of endocarditis based on the following Duke criteria, from The ACC/AHA Guidelines for the Management of Patients with Valvular Heart Disease, JACC, Vol 32, No.5,November 1, 1998:pg1541, Table 21)

Endocarditis is based on the confirmation of either Pathological Criteria or Clinical Criteria.

Diagnosis for Clinical Criteria of Endocarditis must at least meet 1 of the following combinations:

- 2 major criteria or
- 1 major plus 3 minor criteria or
- 5 minor criteria

Pathological Criteria

Microorganisms: culture or histology in a vegetation, in a vegetation that has embolized, or in an intracardiac abscess, OR

Pathological lesions: vegetation or intracardiac abscess present, confirmed by histology showing active endocarditis

OR

Clinical Criteria

Major Criteria

Persistently positive blood cultures:

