Cardiovascular surgical procedure performed for device related complication requiring surgery within 24 hours of onset of adverse event, including events found during scheduled follow-up. If non-urgent surgery was performed within 24 hours of the onset of the adverse event but was not required within this timeframe, it will not be considered "non-elective". Examples of Device Related Complications that may

(Version 2.0; 01 February 2018)

lead to non-elective cardiovascular surgery include, myocardial perforation, Single Leaflet Device Attachment (confirmed by Echo Core Lab), embolization of the TVRS Clip or TVRS System components, iatrogenic atrial septal defect, or the need for tricuspid valve replacement instead of repair due at least in part to the TVRS procedure or the presence of the TVRS Clip.

OPTIMAL MEDICAL THERAPY OR OPTIMAL THERAPY

For Tricuspid Regurgitation: Currently per ESC 2012 guidelines, the only medical therapy described is, "Diuretics reduce congestion. Specific therapy of the underlying disease is warranted." These TR patients typically would have some level of left heart failure by the time TR is detected. Hence, optimal therapy for TR at the present time will follow that defined for patients with left heart failure issues, example mitral regurgitation.

For Mitral Regurgitation: Subjects with current or prior symptoms of heart failure and reduced LVEF should be on stable optimally uptitrated medical therapy recommended according to current guidelines (J Am Coll Cardiol. 2013 Jun 5. doi:pii: S0735-1097(13)02114-1.) as standard of care for heart failure therapy in the United States. This minimally includes an ACE-inhibitor (ACE-I) at stable doses for 30 days prior to subject enrollment in the trial, if tolerated, and a beta blocker (carvedilol, sustained release metoprolol succinate, or bisoprolol) for 90 days prior to subject enrollment in the trial, if tolerated, with a stable up-titrated dose for 30 days prior to subject enrollment in the trial. This also includes an Angiotensin II Receptor Blocker (ARB) at stable doses for 30 days prior to subject enrollment in the trial, if tolerated, when ACE-I is not tolerated. Stable is defined as no more than a 100% increase or a 50% decrease in dose.

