Defined as unilateral TVRS detachment from one leaflet as assessed by the study site and confirmed by the ECL. Reasons for TVRS Detachment include leaflet tearing, TVRS unlocking, TVRS fracture or inadequate TVRS placement. Not included are any fractures or other failures of the TVRS that do not result in TVRS detachment from one or both leaflets.

STROKE/CEREBROVASCULAR ACCIDENT and TIA

Cerebrovascular Accident (Stroke) is defined as an acute episode of focal or global neurological dysfunction caused by brain, spinal cord, or retinal vascular injury as a result of hemorrhage or infarction. Stroke may be classified as ischemic or hemorrhagic with appropriate sub-definitions or as undetermined if there is insufficient information to allow categorization as ischemic or hemorrhagic.

An entity closely related to ischemic stroke is transient ischemic attack (TIA). TIA is defined as a transient episode of focal neurological dysfunction caused by brain, spinal cord, or retinal ischemia, without acute infarction. The difference between TIA and ischemic stroke is the presence of infarction. In the absence of affirmative evidence confirming the presence or absence of infarction, a symptom duration of 24 hours will be used to distinguish TIA from ischemic stroke. By definition, TIA does not produce lasting disability.

The assessment of disability resulting from the stroke will be performed by the modified Rankin Scale (mRS). Assessment of the mRS should occur at all scheduled visits through 24 months and at 90 days after stroke onset. This approach will maximize the detection of new strokes, assist in ongoing evaluation of events previously determined to be TIAs, and provide an accepted and reliable indicator of the long-term impact of a given stroke. A disabling stroke is one that results (at 90 days after stroke onset) in an mRS score of 2 or more and in an increase of at least one mRS category from the individual's pre-stroke baseline. A non-disabling stroke is one that results (at 90 days after stroke onset) in an mRS score of less than 2 or that does not result in an increase of at least one mRS category from an individual's pre-stroke baseline.

Although imaging (typically, MRI for acute and chronic ischemia and haemorrhage, and CT for acute and chronic haemorrhage and chronic ischemia) is often used to supplement the clinical diagnosis of stroke, a diagnosis of stroke may be made on clinical grounds alone.

Diagnostic criteria

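### Appendix II makes single leaflet device attachment depend on a site call and embolization on the site alone, while Protocol 4.3.6 and SAP 1.3.2.6 assign both to the core lab, and no visible text says which rule governs the count.

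*Protocol*

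**What the plan says.** Two parts of the protocol name different assessors for the same device failures.

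- **Protocol Appendix II, Single Leaflet Device Attachment:** "Defined as unilateral TVRS detachment from one leaflet as assessed by the study site and confirmed by the ECL". Two conditions are joined by *and*.
- **Protocol Appendix II, Device Embolization:** "Detachment of the deployed TVRS Clip from the tricuspid leaflets as assessed by the study site". No core-lab role is given.
- **Protocol 4.3.6:** "Echocardiographic endpoints will be assessed by the Echocardiography Core Laboratory (ECL". The list that follows includes "Single Leaflet Device Attachment" and "Embolization of the TVRS Clip or TVRS System components". SAP 1.3.2.6 repeats the assessor and both items and adds no rule of precedence.
- **Protocol 3.2.4:** "the ECL will be responsible for assessing TR severity and echocardiographic analyses at all visits (baseline and follow-ups". The ECL's reading is not limited to echoes that a site has flagged.
- **Protocol 6.8:** when an echo is done at any visit, study-related or not, "echocardiography images should be submitted to the ECL in a timely manner".
- **Protocol Appendix II, non-elective cardiovascular surgery:** SLDA is an example of a device-related complication, and here only core-lab confirmation is named: "Single Leaflet Device Attachment (confirmed by Echo Core Lab".

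SAP 2.2.2 makes the analysis of secondary endpoints descriptive.

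**The concern.** A device-failure rate needs one rule for what counts as a case. Here the same echo can give two answers. Suppose the ECL sees a one-leaflet detachment on a scheduled transthoracic echo or on the 30-day transesophageal echo, and the site did not call it. Under 4.3.6 it is an endpoint event. Under the Appendix II definition the site condition is not met.

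The direction matters because the trial is single-arm and the site that makes the call is also the site that did the implant. If Appendix II is the counting rule for SLDA, independent review works one way only. At stake is how credible the reported SLDA and embolization rates are; SAP 1.3 plans a clinical report for CE Mark and other regulatory submissions.

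**Working it through.** The plan gives no SLDA or embolization rate, so there is no figure to reproduce. The check compares the rules and then illustrates the gap.

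**1. Counts under each rule.** Let S be the events called by the site and E those called by the ECL.

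| Endpoint | Appendix II counts | 4.3.6 and SAP 1.3.2.6 count | 4.3.6 minus Appendix II |
|---|---|---|---|
| SLDA | S and E | E | E without S, never negative |
| Embolization | S | E | (E without S) minus (S without E), either sign |

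For SLDA, the Appendix II count can only equal or fall below the ECL count. For embolization, ECL-only findings drop out under Appendix II, but the site may also hold evidence that echo does not show, so the net direction is not fixed.

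**2. Is the mismatch just the drafting style of Appendix II?** No. Tricuspid valve stenosis is in the same 4.3.6 list, and Appendix II defines it by core-lab measurement. The appendix agrees with 4.3.6 there but not for SLDA or embolization.

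**3. Does any visible text settle it?** Sections 3.2.4, 4.3.6 and 6.8 and SAP 1.3.2.6 point to the ECL. The Appendix II definitions point to the site. Neither document ranks them or says how an ECL-only finding is handled.

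**4. Illustration for SLDA if Appendix II governs.** N = 85 is from Protocol 5.7. The true rate p and the site detection s are assumptions, and ECL detection is assumed perfect.

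- Expected events = N × p
- Expected counted = N × p × s
- Expected missed = N × p × (1 − s)
- P(at least one missed) = 1 − [1 − p(1 − s)]^N

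| p | Expected events | Counted at s = 60% / 80% / 90% | P(at least one missed) at s = 60% / 80% / 90% |
|---|---|---|---|
| 3% | 2.6 | 1.5 / 2.0 / 2.3 | 0.64 / 0.40 / 0.23 |
| 5% | 4.3 | 2.6 / 3.4 / 3.8 | 0.82 / 0.57 / 0.35 |
| 10% | 8.5 | 5.1 / 6.8 / 7.7 | 0.97 / 0.82 / 0.57 |

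Expected missed events run from 85 × 0.03 × 0.10 = 0.3 to 85 × 0.10 × 0.40 = 3.4. The relative undercount is 1 − s by construction, so it restates an assumption and is not a finding. If 4.3.6 governs, with the same perfect ECL detection, the loss is zero.

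**The case against.** The strongest reply is that the endpoint sections, not a glossary, define what is reported. On that reading the ECL assesses SLDA and embolization at every visit, also receives echoes from unscheduled visits, and reports what it sees. The Appendix II wording would then do no harm. This stands as far as it goes: a reader might infer that device failures missed by the site are certainly left out, and the documents do not support that. They leave the rule open.

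A reader might also infer that the site must report first and so decides which detachments reach independent review. No reporting order is stated, and the images go to the ECL regardless. What Appendix II makes conditional is meeting the definition, not access to the images.

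Other safeguards exist. Sites must evaluate device integrity in implanted subjects (Protocol 6.5) and report device deficiencies within 3 calendar days (7.3.3). The Clinical Events Committee can receive events identified by safety personnel as well as by investigators (8.1). These lower the chance of a miss but do not settle the definition, and Protocol 11.8.3 has that committee adjudicate by the protocol's own definitions.

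A site role in embolization is reasonable, since Appendix II allows diagnosis by fluoroscopy or x-ray, which an echo core lab may not receive. The fix keeps it.

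Finally, the ECL and Clinical Events Committee manuals are not supplied and parts of the protocol are not shown, so a reconciling rule may exist there. The protocol and SAP should still agree on the assessor.

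**Conclusion.** The inconsistency is real and should be reconciled. If Appendix II is applied, events seen only by the ECL may go uncounted, and the SLDA rate could be biased downward. That is conditional on which text governs. The size cannot be derived from the documents, and the figures in the working rest wholly on assumed rates.

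The consequence is limited to secondary, descriptive device-failure rates. No performance goal or hypothesis test depends on them.

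A reader might infer that the primary safety endpoint is biased too, because SLDA appears as an example under non-elective surgery. That is not shown. SLDA and embolization are not components of the major adverse event composite. The surgery definition asks only for core-lab confirmation of SLDA, and that component needs surgery required within 24 hours of onset, which a detachment unnoticed at the site would hardly prompt.

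**What to change.** State one counting rule in Appendix II and carry it into Protocol 4.3.6, SAP 1.3.2.6 and the ECL and eCRF instructions:

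- **SLDA:** count one-leaflet detachment identified by the ECL on any submitted echo, whether or not the site called it. A site suspicion remains an additional trigger for ECL review.
- **Embolization:** count it when identified by the ECL on echo, or by the site on non-echo evidence (fluoroscopy, x-ray, surgery or autopsy).
- **Disagreements:** report the number of site-only and ECL-only calls for each endpoint.

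The cost is mainly wording, since the ECL already has echo analyses at all visits. The reported rates may turn out slightly less favourable.

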APPENDIX V: MONITORING EXPOSURE TO IONIZING RADIATION

(1) Implanting Investigator Training

Prior to treating patients with the TVRS Clip, all implanting investigators shall complete the TVRS therapy training curriculum, including training to this section of the study Clinical Investigational Plan.

(2) Pre, Peri and Post-TVRS Procedure

The implanting investigator shall be responsible for patient radiation levels and shall ensure that radiation dose accumulation is continuously monitored during the procedure (NCRP 2010). Documentation of dose levels shall be in accordance with the individual requirements of the respective institution's quality management program. In addition, the following shall apply:

a. Dose Measurements required for TVRS procedure

Where the fluoroscopy system has the functionality for the output of data, the following dose measurements shall be recorded in the subject records and reported in the eCRFs.

- Total fluoro time: to be reported in minutes
- Total number of fluoro frames: to be reported as whole numbers, no associated units
- Air kerma-area product (PkA) (dose area product): to be reported in Gy cm2
- Air kerma at the reference point (Ka,r): to be reported in Gy
- Peak skin dose (Dskin, max): to be reported in Gy

Investigational centers that are unable to provide the information due to the limitations oftheir fluoroscopy systems are exempt from the reporting requirements.

b. Substantial Radiation Dose Level (SRDL)

The SRDL is a trigger level to initiate follow-up of a radiation dose that may produce a clinically relevant injury in an average patient. Procedures, such as the MitraClip procedure, that are performed using biplane fluoroscopy systems are a special situation because the dose received from each plane should be considered independently when the fields do not overlap. When they do overlap, the doses are additive and if it is uncertain whether the fields overlap, it should be assumed that they do.

The following are suggested values for first and subsequent notifications and the SRDL based upon a 100cm² field at the subject's skin. The implanting investigator should adjust the notifications and the SRDL proportionally to the actual procedural field size.

When the SRDL has been exceeded, the implanting investigator shall document the dose exceeded and the justification for the radiation dose level used (NCRP 2010).

(Version 2.0; 01 February 2018)

Suggested values for first and subsequent notifications and the SRDL (NCRP 2010)

Dose Metric	First Notification	Subsequent Notifications (increments)	SRDL
$D_{ m skin,max}$	2 Gy	0.5 Gy	3 Gy
Ka,r	3 Gy	1 Gy	5 Gy
P_{KA}	300 Gy cm ² *	100 Gy cm ² *	500 Gy cm ² *
Fluoroscopy time	30 min	15 min	60 min

^{*} Assuming a 100 cm² field at the subject's skin. For other field sizes, the *P*_{KA} values should be adjusted proportionally to the actual procedural field size (*e.g.*, for a field size of 50 cm², the SRDL value for *P*_{KA} would be 250 Gy cm²).

(1) Acute Evaluation

Subjects should be advised of the possibility of a skin injury due to a tissue reaction, and should be told to examine the beam entrance site at 2-4 weeks after the procedure and report any observations to the site Principal Investigator or designee During the physical examination at the 30-day follow-up clinic visit, the site Principal Investigator or designee shall examine the integrity of the subject's skin at or near the beam entrance site. If there is evidence of skin injury, the site Principal Investigator or designee shall report it as an adverse event in accordance with the adverse event reporting requirements.

(2) Long-term Evaluation

The site Principal Investigator or designee is responsible for the ongoing collection and monitoring of radiation doses. An examination of the subject's skin at or near the beam entrance site shall be performed by the site Principal Investigator or designee. If skin injury resulting from radiation exposure during the MitraClip procedure is ongoing beyond the 30-day follow-up, the site Principal Investigator or designee should arrange for follow-up care. Observations of skin injury shall be reported as an adverse event in accordance with the adverse event reporting requirements.

(Version 2.0; 01 February 2018)

APPENDIX VI: SOCIETY

6 MINUTE WALK TEST GUIDELINES - AMERICAN THORACIC

Six minute walk test will be performed as outlined in the published guidelines by the American Thoracic Society.

ATS Committee on Proficiency Standards for Clinical Pulmonary Function Laboratories.. ATS statement: guidelines for the six-minute walk test. Am J Respir Crit Care Med. 2002 Jul 1;166(1):111-7.

(Version 2.0; 01 February 2018)

American Thoracic Society

ATS Statement: Guidelines for the Six-Minute Walk Test

THIS OFFICIAL STATEMENT OF THE AMERICAN THORACIC SOCIETY WAS APPROVED BY THE ATS BOARD OF DIRECTORS MARCH 2002.

CONTENTS

Purpose and Scope
Background
Indications and Limitations
Contraindications
Safety Issues
Technical Aspects of the 6-Minute Walk Test
Required Equipment
Patient Preparation
Measurements
Quality Assurance
Interpretation
References

PURPOSE AND SCOPE

This statement provides practical guidelines for the 6-minute walk test (6MWT). Specifically, it reviews indications, details factors that influence results, presents a brief step-by-step protocol, outlines safety measures, describes proper patient preparation and procedures, and offers guidelines for clinical interpretation of results. These recommendations are not intended to limit the use of alternative protocols for research studies. We do not discuss the general topic of clinical exercise testing.

As with other American Thoracic Society statements on pulmonary function testing, these guidelines come out of a consensus conference. Drafts were prepared by two members (P.L.E. and R.J.Z.) and were based on a comprehensive Medine literature search from 1970 through 2001, augmented by suggestions from other committee members. Each draft responded to comments from the working committee. The guidelines follow previously published methods as closely as possible and provide a rationale for each specific recommendation. The final recommendations represent a consensus of the committee. The committee recommends that these guidelines be reviewed in five years and in the meantime encourages further research in areas of controversy.

BACKGROUND

There are several modalities available for the objective evaluation of functional exercise capacity. Some provide a very complete assessment of all systems involved in exercise performance (high tech), whereas others provide basic information but are low tech and are simpler to perform. The modality used should be chosen based on the clinical question to be addressed and on available resources. The most popular clinical exercise tests in order of increasing complexity are stair climbing, a 6MWT, a shuttle-walk test, detection of exercise-induced asthma, a cardiac stress test (e.g., Bruce protocol), and a cardio-

Am J Respir Crit Care Med Vol 166. pp 111–117, 2002 DOI: 10.1164/rccm.166/1/111 Internet address: www.atsjournals.org pulmonary exercise test (1, 2). Other professional organizations have published standards for cardiac stress testing (3, 4).

Assessment of functional capacity has traditionally been done by merely asking patients the following: "How many flights of stairs can you climb or how many blocks can you walk?" However, patients vary in their recollection and may report overestimations or underestimations of their true functional capacity. Objective measurements are usually better than self-reports. In the early 1960s, Balke developed a simple test to evaluate the functional capacity by measuring the distance walked during a defined period of time (5). A 12-minute field performance test was then developed to evaluate the level of physical fitness of healthy individuals (6). The walking test was also adapted to assess disability in patients with chronic bronchitis (7). In an attempt to accommodate patients with respiratory disease for whom walking 12 minutes was too exhausting, a 6-minute walk was found to perform as well as the 12-minute walk (8). A recent review of functional walking tests concluded that "the 6MWT is easy to administer, better tolerated, and more reflective of activities of daily living than the other walk tests" (9).

The 6MWT is a practical simple test that requires a 100-ft hallway but no exercise equipment or advanced training for technicians. Walking is an activity performed daily by all but the most severely impaired patients. This test measures the distance that a patient can quickly walk on a flat, hard surface in a period of 6 minutes (the 6MWD). It evaluates the global and integrated responses of all the systems involved during exercise, including the pulmonary and cardiovascular systems, systemic circulation, peripheral circulation, blood, neuromuscular units, and muscle metabolism. It does not provide specific information on the function of each of the different organs and systems involved in exercise or the mechanism of exercise limitation, as is possible with maximal cardiopulmonary exercise testing. The self-paced 6MWT assesses the submaximal level of functional capacity. Most patients do not achieve maximal exercise capacity during the 6MWT; instead, they choose their own intensity of exercise and are allowed to stop and rest during the test. However, because most activities of daily living are performed at submaximal levels of exertion, the 6MWD may better reflect the functional exercise level for daily physical activities.

INDICATIONS AND LIMITATIONS

The strongest indication for the 6MWT is for measuring the response to medical interventions in patients with moderate to severe heart or lung disease. The 6MWT has also been used as a one-time measure of functional status of patients, as well as a predictor of morbidity and mortality (see Table 1 for a list of these indications). The fact that investigators have used the 6MWT in these settings does not prove that the test is clinically useful (or the best test) for determining functional capacity or changes in functional capacity due to an intervention in patients with these diseases. Further studies are necessary to determine the utility of the 6MWT in various clinical situations.

(Version 2.0; 01 February 2018)

AMERICAN JOURNAL OF RESPIRATORY AND CRITICAL CARE MEDICINE VOL 166 2002

112

Formal cardiopulmonary exercise testing provides a global assessment of the exercise response, an objective determination of functional capacity and impairment, determination of the appropriate intensity needed to perform prolonged exercise, quantification of factors limiting exercise, and a definition of the underlying pathophysiologic mechanisms such as the contribution of different organ systems involved in exercise. The 6MWT does not determine peak oxygen uptake, diagnose the cause of dyspnea on exertion, or evaluate the causes or mechanisms of exercise limitation (1, 2). The information provided by a 6MWT should be considered complementary to cardiopulmonary exercise testing, not a replacement for it. Despite the difference between these two functional tests, some good correlations between them have been reported. For example, a significant correlation (r = 0.73) between 6MWD and peak oxygen uptake has been reported for patients with end-stage lung diseases (36, 37).

In some clinical situations, the 6MWT provides information that may be a better index of the patient's ability to perform daily activities than is peak oxygen uptake; for example, 6MWD correlates better with formal measures of quality of life (38). Changes in 6MWD after therapeutic interventions correlate with subjective improvement in dyspnea (39, 40). The reproducibility of the 6MWD (with a coefficient of variation of approximately 8%) appears to be better than the reproducibility of 1-second forced expiratory volume in patients with chronic obstructive pulmonary disease (COPD) (8, 41–43). Questionnaire indices of functional status have a larger short-term variability (22–33%) than does the 6MWD (37).

The shuttle-walking test is similar to the 6MWT, but it uses an audio signal from a tape cassette to direct the walking pace of the patient back and forth on a 10-m course (44–47). The walking speed is increased every minute, and the test ends when the patient cannot reach the turnaround point within the required time. The exercise performed is similar to a symptom-limited, maximal, incremental treadmill test. An advantage of the shuttle walking test is that it has a better correlation with peak oxygen uptake than the 6MWD. Disadvantages include less validation, less widespread use, and more potential for cardiovascular problems.

CONTRAINDICATIONS

Absolute contraindications for the 6MWT include the following: unstable angina during the previous month and myocar-

TABLE 1. INDICATIONS FOR THE SIX-MINUTE WALK TEST

Pretreatment and posttreatment comparisons Lung transplantation (9, 10) Lung resection (11) Lung volume reduction surgery (12, 13) Pulmonary rehabilitation (14, 15) COPD (16-18) Pulmonary hypertension Heart failure (19, 20) Functional status (single measurement) COPD (21, 22) Cystic fibrosis (23, 24) Heart failure (25-27) Peripheral vascular disease (28, 29) Fibromyalgia (30) Older patients (31) Predictor of morbidity and mortality Heart failure (32, 33) COPD (34, 35)

Primary pulmonary hypertension (10, 36)

Definition of abbreviation: COPD = chronic obstructive pulmonary disease.

dial infarction during the previous month. Relative contraindications include a resting heart rate of more than 120, a systolic blood pressure of more than 180 mm Hg, and a diastolic blood pressure of more than 100 mm Hg.

Patients with any of these findings should be referred to the physician ordering or supervising the test for individual clinical assessment and a decision about the conduct of the test. The results from a resting electrocardiogram done during the previous 6 months should also be reviewed before testing. Stable exertional angina is not an absolute contraindication for a 6MWT, but patients with these symptoms should perform the test after using their antiangina medication, and rescue nitrate medication should be readily available.

Rationale

Patients with the previously mentioned risk factors may be at increased risk for arrhythmias or cardiovascular collapse during testing. However, each patient determines the intensity of their exercise, and the test (without electrocardiogram monitoring) has been performed in thousands of older persons (31, 48–50) and thousands of patients with heart failure or cardiomyopathy (32, 51, 52) without serious adverse events. The contraindications listed previously here were used by study investigators based on their impressions of the general safety of the 6MWT and their desire to be prudent, but it is unknown whether adverse events would occur if such patients performed a 6MWT; they are, therefore, listed as relative contraindications.

SAFETY ISSUES

- Testing should be performed in a location where a rapid, appropriate response to an emergency is possible. The appropriate location of a crash cart should be determined by the physician supervising the facility.
- Supplies that must be available include oxygen, sublingual nitroglycerine, aspirin, and albuterol (metered dose inhaler or nebulizer). A telephone or other means should be in place to enable a call for help.
- 3. The technician should be certified in cardiopulmonary resuscitation with a minimum of Basic Life Support by an American Health Association-approved cardiopulmonary resuscitation course. Advanced cardiac life support certification is desirable. Training, experience, and certification in related health care fields (registered nurse, registered respiratory therapist, certified pulmonary function technician, etc.) are also desirable. A certified individual should be readily available to respond if needed.
- 4. Physicians are not required to be present during all tests. The physician ordering the test or a supervising laboratory physician may decide whether physician attendance at a specific test is required.
- If a patient is on chronic oxygen therapy, oxygen should be given at their standard rate or as directed by a physician or a protocol.

Reasons for immediately stopping a 6MWT include the following: (1) chest pain, (2) intolerable dyspnea, (3) leg cramps, (4) staggering, (5) diaphoresis, and (6) pale or ashen appearance.

Technicians must be trained to recognize these problems and the appropriate responses. If a test is stopped for any of these reasons, the patient should sit or lie supine as appropriate depending on the severity or the event and the technician's assessment of the severity of the event and the risk of syncope. The following should be obtained based on the judgment of the technician: blood pressure, pulse rate, oxygen saturation, and a physician evaluation. Oxygen should be administered as appropriate.

Abbott Vascular

TRILUMINATE Trial

(Version 2.0; 01 February 2018)

American Thoracic Society 113

TECHNICAL ASPECTS OF THE 6MWT

Location

The 6MWT should be performed indoors, along a long, flat, straight, enclosed corridor with a hard surface that is seldom traveled. If the weather is comfortable, the test may be performed outdoors. The walking course must be 30 m in length. A 100-ft hallway is, therefore, required. The length of the corridor should be marked every 3 m. The turnaround points should be marked with a cone (such as an orange traffic cone). A starting line, which marks the beginning and end of each 60-m lap, should be marked on the floor using brightly colored tape.

Rationale. A shorter corridor requires patients to take more time to reverse directions more often, reducing the 6MWD. Most studies have used a 30-m corridor, but some have used 20- or 50-m corridors (52–55). A recent multicenter study found no significant effect of the length of straight courses ranging from 50 to 164 ft, but patients walked farther on continuous (oval) tracks (mean 92 ft farther) (54).

The use of a treadmill to determine the 6MWD might save space and allow constant monitoring during the exercise, but the use of a treadmill for 6-minute walk testing is not recommended. Patients are unable to pace themselves on a treadmill. In one study of patients with severe lung disease, the mean distance walked on the treadmill during 6 minutes (with the speed adjusted by the patients) was shorter by a mean of 14% when compared with the standard 6MWD using a 100-ft hallway (57). The range of differences was wide, with patients walking between 400–1,300 ft on the treadmill who walked 1,200 ft in the hallway. Treadmill test results, therefore, are not interchangeable with corridor tests.

REQUIRED EQUIPMENT

- 1. Countdown timer (or stopwatch)
- 2. Mechanical lap counter
- 3. Two small cones to mark the turnaround points
- 4. A chair that can be easily moved along the walking course
- 5. Worksheets on a clipboard
- 6. A source of oxygen
- Sphygmomanometer
- 8. Telephone
- 9. Automated electronic defibrillator

PATIENT PREPARATION

- 1. Comfortable clothing should be worn.
- 2. Appropriate shoes for walking should be worn.
- Patients should use their usual walking aids during the test (cane, walker, etc.).
- 4. The patient's usual medical regimen should be continued.
- A light meal is acceptable before early morning or early afternoon tests.
- Patients should not have exercised vigorously within 2 hours of beginning the test.

MEASUREMENTS

- Repeat testing should be performed about the same time of day to minimize intraday variability.
- A "warm-up" period before the test should not be performed.
- 3. The patient should sit at rest in a chair, located near the starting position, for at least 10 minutes before the test starts. During this time, check for contraindications, measure pulse and blood pressure, and make sure that clothing and shoes are appropriate. Compete the first portion of the worksheet (see the APPENDIX).

